Aim 1. Determine the feasibility and usability of (1) EMA to assess self-report residential environmental exposures and asthma symptoms, (2) home monitoring of environmental exposures (VOCs, PM_{2.5}), and lung function (home spirometry, FEV₁% predicted).

Aim 2a. Assess the frequency and degree of residential environmental exposures (e.g., disinfectants/cleaners, second-hand smoke) via (1) self-reported data, and (2) home monitoring objective measures.

Aim 2b. Assess the level of asthma control as indicated by self-reported asthma symptoms and lung function.

Aim 3. Explore associations of self-reported and objective measures of residential environmental exposures with self-reported and objective measures of asthma control.

Findings from this study will provide preliminary data for a powered study to develop innovative intervention strategies for those with asthma addressing the impact of changes in environmental exposures related to COVID-19 and enhancing our preparedness for future infectious disease outbreaks. This has implications for risk reduction in individuals with asthma to help improve asthma self-management using personal monitors and sensors for individually tailored exposure profiles.

SIGNIFICANCE

Asthma is a disease of chronic airway inflammation and affects 1 in 12 adults in the US.¹ Despite effective treatments for asthma, it is estimated that more than 60% of adults with asthma have uncontrolled symptoms.² Poorly controlled asthma increases the risks of severe asthma exacerbations which may result in missed work days, emergency room visits, and hospitalizations.¹³ The 20 year direct costs related to uncontrolled asthma exceed \$300 billion thus the burden of uncontrolled asthma is substantial.³

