In summary, the impact of home disinfectant use and particulate matter on adult asthma outcomes, particularly during the COVID-19 pandemic, demands further investigation. The home environment is an unregulated space where individuals and families make unique purchasing and cleaning decisions driven by tradition, finances, social and media influences. Existing research on VOCs and particulate matter provides a strong scientific premise for further exploration of these exposures in the home as the COVID-19 pandemic continues to actively unfold. This research can provide evidence-based guidance for home disinfectant use during a pandemic for those with asthma. Research efforts focused on indoor home environments are essential to understand the possible extent of exposures that can impact asthma outcomes in a time when home and healthcare resources (social and financial) continue to be strained. To describe our research trajectory, we illustrate the goals of our feasibility study and the impacts we intend to accomplish using the Translational Research Framework.^{58,59} This feasibility study will assess residential exposures of disinfectants and particulates with the goal of reducing exposures and improving asthma outcomes (Figure 1).

INNOVATION

The proposed feasibility study is innovative in several ways. First, the study addresses how increased cleaning and disinfecting practices associated with a novel virus could impact asthma control in those with asthma. Second, we uniquely use EMA to examine the effects of environmental triggers on adult asthma symptoms in real time, allowing us to capture participant engagement in their own home environment. Third, we will use and integrate innovative technologies to collect self-report and objective residential exposure data (VOCs, PM_{2.5}) in real time and link these data with self-report (EMA) and objective data on asthma control (spirometer). Fourth, this study focuses on adults with sub-optimal asthma control, a population also at higher risk for complications from COVID-19.

APPROACH

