Research Design. This study will evaluate the feasibility and usability of assessing real-time residential environmental exposures (VOCs/PM_{2.5}), asthma symptoms, and lung function using an innovative combination of commercially available technology (Aim 1).⁶⁰ In addition, we will use observational design to explore the unintended effects of these residential environmental exposures on adults with poorly controlled asthma in the era of COVID-19 (Aims 2 & 3).

Sample. Eligibility criteria include GCAS participants who: (1) indicated willingness to be contacted for future research, (2) reported high use of disinfectant/cleaning products since COVID-19 (≥ 5 per week), and current ACT ≤ 19 . Non-US residents and non-English speakers will be excluded. We will strive to have at least 20% of the sample representing minority populations. Fifty individuals meeting these criteria will be randomly selected and invited to participate in this study using their preferred contact method (94% indicated email). Interested individuals will be directed to a REDCap survey link to confirm willingness to participate, verify eligibility, and provide current contact information. We will randomly select replacements if no response is received after 2 contact attempts over two weeks or lack of interest is indicated.

Data collection methods. Three innovative data collection methods will be integrated in this feasibility study: Ecological Momentary Assessment (EMA) downloaded to participants' smartphone, Awair Omni Indoor Air Quality Monitor®, and Zephyr_x Spirometer.

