4. During the 14-day data collection period, data from the EMA will be collected using EMA software platform on a personal smartphone (iOS or Android) and EMA software platform.⁷³ Each morning, participants will receive an EMA survey concerning asthma symptoms and a reminder to use their spirometer. Additionally, EMA surveys addressing disinfectant use, asthma symptoms, and spirometry will occur randomly twice/day (6am – 10pm) or tailored for those working off hours (Appendix).
5. A custom interface between the EMA platform and the Awair indoor air quality monitor will alert participants when levels of indoor VOCs or particulates are detected outside the optimal range (Table 1). The air quality monitor will communicate with the EMA platform using publicly available application programming interface (api). Upon notification from the Awair, the EMA will signal the participant to complete a brief survey on disinfectant use/air particulate exposure (depending on the alert), current asthma symptoms, and proximity to the Awair (Appendix). The EMA will then direct participants to use the spirometer. Participants experiencing symptoms will be guided to follow their asthma action plan/provider instructions.
6. Thirty minutes after VOC/PM_{2.5} notification, a second EMA notification will be sent for participants to complete a survey on mitigation strategies, respiratory outcomes, and spirometry use if not already completed (Figure 4).
7. Research personnel will monitor use of these devices/apps and contact participants if a 24-hour gap in data is noted to address concerns and determine acceptability. Research team members will check-in with each participant at about the 7-day mark to address technical concerns and ease of use.

8. At the end of the 14 days, participants will complete a short acceptability, appropriateness, and feasibility REDCap survey. A random sample of 20 participants will be interviewed to provide further insights.
9. Participants will be asked to return the Awair in the provided mailer. The Awair will be fully disinfected per manufacturer's directions. Participants will keep the Zephyr_x spirometer as an incentive.

Baseline Measures

The following measures will be administered at baseline via REDCap:

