1. *Adult Asthma History* includes 5 items adapted from the Behavioral Risk Factor Surveillance System Survey.⁷⁴ Four items address participants' recent contact with healthcare professionals for asthma since COVID-19. The final item addresses changes in routine work/activities due to asthma since COVID-19.
2. *Asthma Control Test (ACT)*. The ACT includes 5 items addressing: asthma symptoms, use of rescue medications, and effect of asthma on daily functioning. Responses are summed for total ACT score.^{75,76}
3. *Airborne Exposures*. The 7 items from the PROMISSM Pool V1.0 Dyspnea Airborne Exposure address airborne allergens, pollutants, smoke, pets, and use of pesticides using Yes:No response options.⁷⁷
4. *Adult Asthma Adherence Questionnaire*,TM includes 5 items on following their prescribed asthma medication plan and barriers to following that plan.⁷⁸
5. *Health and Demographics* includes items such as self-rated physical health, comorbidities, height/weight, age, education, ZIP code, smoking status, and COVID-19 prevention practices, and COVID-19 exposure/infection status.
6. *Home Environmental Exposure* data will be gathered including home type, # of occupants, vacuum with HEPA filter, cleaning practices, cleaning products, air filter, heating, ventilation, smoke exposures, hand washing practices, pests, hobbies, odors, indoor plants, printers, flooring, and stove type.^{79,80}

We will also measure the following psychometrically valid measures as potential confounders:

7. *Emotional Distress-Anxiety and Depression PROMIS Short Forms 4a* assess anxiety and depression levels within the last 7 days (4 items). Higher scores indicate higher severity of anxiety or depression.^{81,82}
8. *Emotional Support*, PROMIS_SF_V2 Short Form 4A measures perceived feelings of support, being cared for and valued (4 items).⁸³ Higher score indicating a higher perceived emotional support.
9. *Perceived stress scale* includes 4 items measuring the degree to which situations in one's life are appraised as stressful.⁸⁴⁻⁸⁶ Higher scores indicate an increased level of perceived stress.

EMA survey items (See Appendix).

- *Asthma symptoms* (trouble breathing, wheezing, coughing, other symptoms [Yes:No]) assessed each time participants are asked to complete an EMA survey.
- *Random EMA surveys (twice/day)* assess use of disinfectants/cleaners in last 2 hours (Yes:No) if Yes, the type, brand, and asthma symptoms are queried.

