We will also assess the duration the indoor air quality monitor is used by each participant. The quantitative participant feasibility assessment of acceptability, appropriateness, and feasibility will be analyzed descriptively. In addition, we will examine differences in use/acceptance by participant characteristics (e.g., age, asthma symptoms, overall health, education, etc). Qualitative interview data will be transcribed, uploaded into Dedoose qualitative analysis software for content analysis.

Aim 2a: We will collect baseline data on the current frequency and degree of disinfectants/cleaners and exposure to environmental triggers (e.g., secondhand smoke). We will capture real-time self-reported data on disinfectant use throughout the study period. We will determine the prevalence of disinfectant/cleaner use and frequency (% EMA prompts at which disinfectant/cleaner use is reported). We will obtain data from the Awair dashboard to determine the number of times VOCs and PM_{2.5} levels exceed optimal levels, average daily levels, average levels per time period, and fluctuations in VOC and PM_{2.5}. We will identify possible environmental triggers that contribute to high levels of VOCs and PM_{2.5} leading to event-contingent prompts.

[figure not shown]
Aim 2b: We will determine baseline level of asthma control as measured by the ACT. We will use EMA to determine the level of asthma control over the study period as indicated by (a) asthma symptoms reported at each prompt and over the 14 days; (b) number of time-periods during which an EMA prompt is sent and participants report asthma symptoms; and (c) lung function as measured by FEV₁% predicted at each prompt. Asthma control will also be evaluated using EMA by exploring differences in variability in lung function.

Aim 3: Data collected using the EMA approach are multilevel with time windows (level 1) nested with individuals (level 2). The exposure variables will include: (1) Baseline self-reported use and frequency of disinfectant/cleaner use and PM_{2.5} exposures; (2) Number of times VOC and PM_{2.5} levels exceed the threshold for the optimal readings per week; and (3) Average scores of VOC and PM_{2.5} levels in the time windows considered in the analysis. The outcome variables we will consider include occurrence of any asthma symptoms, inhaler use, and FEV₁% predicted (within 30 minutes of each EMA prompt).

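### Aim 3 names no prompt-level or window-level self-reported exposure, so the EMA reports of recent disinfectant use have no stated place in the association models

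*Combined protocol and SAP*

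**What the plan says.** Specific Aims, Aim 3, sets out to "Explore associations of self-reported and objective measures of residential environmental exposures with self-reported and objective measures of asthma control". The Innovation section says "we uniquely use EMA to examine the effects of environmental triggers on adult asthma symptoms in real time", and promises self-reported as well as monitored exposure data, collected in real time and linked to asthma control.

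The Data Analysis section for Aim 3 introduces its exposures as what they will include, and lists three:

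1. "Baseline self-reported use and frequency of disinfectant/cleaner use and PM_{2.5} exposures";
2. weekly counts of monitor readings above the optimal range;
3. monitor averages of VOC and PM2.5 in the time windows.

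The models have time windows at level 1 and individuals at level 2.

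Procedures, step 4, states that "EMA surveys addressing disinfectant use, asthma symptoms, and spirometry will occur randomly twice/day". Under EMA survey items, the random surveys "assess use of disinfectants/cleaners in last 2 hours (Yes:No"). Symptoms are "assessed each time participants are asked to complete an EMA survey". In Data Analysis, the only stated use of EMA-reported disinfectant use is in Aim 2a, as a percentage of prompts. A general rule ahead of the aims says that data from answered random prompts will be considered, without giving them a role in Aim 3.

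**The concern.** A baseline item is constant within a person. Whatever multilevel model is fitted, its coefficient compares people who use more with people who use less, and so mixes use with every other difference between those people and their homes. The entry criterion, "reported high use of disinfectant/cleaning products since COVID-19 (≥ 5 per week"), may also narrow that comparison, although it refers to use reported in the online survey and not to use during the 14 days.

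EMA is suited to a different question: in the same person, are symptoms more frequent, or FEV1% predicted lower, at prompts with recent use than at prompts without it? The data for that contrast are already planned, but the plan does not name the variable or say at which level it enters. Those choices would then be made after the data are seen. The monitor does not replace the item: it measures total VOC and PM2.5, whereas the EMA item identifies product use, with type and brand.

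**Working it through.** The plan gives no figure on this point to reproduce. The check is a comparison of the text, followed by counts and an illustration of precision.

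**Named Aim 3 exposures by source and level**

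| Exposure | Source | Varies within person? |
|---|---|---|
| Baseline use and frequency, PM2.5 exposures | Self-report | No |
| Weekly count of out-of-range readings | Monitor | By week only |
| Window-average VOC and PM2.5 | Monitor | Yes |
| EMA-reported use in last 2 hours | Self-report | Yes, but not named |

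The rest of the Aim 3 text does not fill the gap. The level-1 covariates are time of day and day of week, and the lag analysis starts at a monitor-triggered prompt.

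**Counts** (50 participants, 14 days, 2 random prompts a day, four 4-hour windows a day, all from the documents)

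- Random-prompt reports: 2 x 14 = 28 per person; 28 x 50 = 1,400 at most. Each baseline item gives 50 values.
- Windows: 4 x 14 = 56 per person; 56 x 50 = 2,800. At most 28 of 56 (50%) can hold a random prompt.

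**Expected Yes reports (illustration).** Current use is not given, so assume u = 2, 5 or 14 uses a week, at random over 16 h x 7 d = 112 h, with prompts uniform from 6 a.m. to 10 p.m. and full response. Let x = 2u/112 and f = 1 - exp(-x). Prompts in the first 2 of the 16 hours look back partly to hours with no assumed use, so

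Yes share = (14/16) f + (2/16)(1 - f/x).

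| u | x | f | Yes share | x 1,400 | Per person |
|---|---|---|---|---|---|
| 2 | 0.0357 | 0.0351 | 0.0329 | 46 | 0.9 |
| 5 | 0.0893 | 0.0854 | 0.0802 | 112 | 2.2 |
| 14 | 0.2500 | 0.2212 | 0.2079 | 291 | 5.8 |

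**Precision (illustration).** Simulated within-person (conditional) logistic regression: 50 people x 28 prompts, no true effect, between-person SD 1.5 on the logit scale. The two cases are 60% response with symptoms at 20% of prompts, and 90% response with symptoms at 40%. The interval multiplier is exp(1.96 x SE).

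| u | SE of log odds ratio | Multiplier |
|---|---|---|
| 2 | 0.560 and 0.386 | 3.0 and 2.1 |
| 5 | 0.370 and 0.250 | 2.1 and 1.6 |
| 14 | 0.248 and 0.168 | 1.6 and 1.4 |

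These SEs used the full 2-hour share f. The smaller Yes share raises them by about 3% (at u = 2, the square root of 49.1/46.1 is 1.03). The largest multiplier then becomes about 3.1, and the others move by less than 0.1. At 2 uses a week only about 17 to 28 of the 50 participants inform the estimate. Clustering of use into cleaning sessions would lower precision further.

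**The case against.** The strongest reply is that the list is open. It says what the exposures will include, a general rule says random-prompt data will be considered, and the model is already set at window level. This stands: a reader might infer that EMA self-report is excluded from Aim 3, and the documents do not support that. A reader might also infer that Aim 3 has no real-time analysis at all. That fails too, because the window-average monitor levels vary within person and there is a lag analysis. What remains is that no time-varying self-reported exposure is named.

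Two other readings of item (1) are possible. Frequency could mean the Aim 2a percentage of prompts, but used as a person's frequency that is still one value each. Baseline could refer to the baseline EMA prompts in the data-handling rule. However, Aim 2a separates baseline data from real-time self-report, and the morning survey is described as covering symptoms and a spirometer reminder only.

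It can also be said that the study is a feasibility study, that Aim 3 is exploratory, and that the precision figures rest on assumptions. All true. They show what the item might yield and do not measure a defect.

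Finally, the phrase "if Yes, the type, brand, and asthma symptoms are queried" might suggest that symptoms are asked only after a Yes, which would leave no comparison prompts. The other EMA bullet, Procedures step 4 and Aim 2b all have symptoms asked at each prompt, and the Appendix is not in the supplied text. This is at most a one-line clarification.

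**Conclusion.** The point holds as a gap in specification. The named Aim 3 exposures include no prompt-level or window-level self-report, so following the list would leave self-reported exposure with between-person associations only, while up to 1,400 repeated reports (28 per person) have a stated descriptive use alone. The text supports this without any assumption beyond 50 enrolled participants and full prompting. It does not make the planned models invalid, and the monitored exposures are not affected by it.

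The likely return depends on current use, response, symptom frequency and between-person spread, none of which the documents give. Over the assumed ranges, the result runs from a weak estimate (a multiplier of about 3 at 2 uses a week) to a reasonably informative one (about 1.4 at 14 uses a week). The change is worth making because it is inexpensive and delivers what the aims promise.

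**What to change.** In the Aim 3 analysis text:

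- Add EMA-reported disinfectant/cleaner use in the last 2 hours at random prompts (Yes/No) as a level-1 exposure. Link it to symptoms, FEV1% predicted and, where recorded, inhaler use at the same prompt.
- Enter it as participant mean (level 2) plus deviation from that mean (level 1), so that momentary and between-person associations are reported separately. Do the same for the window averages of VOC and PM2.5.
- Treat windows without an answered random prompt as missing on this exposure, not as No.
- Base the main estimate on random prompts, because alert prompts are selected on high readings. Include disinfectant use reported at event-contingent prompts in a sensitivity analysis.
- Keep the baseline items as level-2 variables, including self-reported PM2.5 exposure, since EMA asks about particulate sources only after an alert.
- Report the results as exploratory, with confidence intervals and the numbers of exposed prompts and informative participants. State that an association at the same prompt does not show that use came before symptoms.
- Clarify in one line that symptoms are asked at every random prompt, if that is the intent.

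The cost is a few lines of wording and no new data collection. The downside is a few more exploratory estimates, which will be imprecise if use is low.

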Preliminary work - Global COVID-19 and Asthma Study (GCAS). The proposed study builds on data collected from the GCAS, an ongoing cross-sectional online survey we launched in May 2020 to examine how the COVID-19 pandemic affected the prevalence of disinfectant use among adults with asthma and to assess the associations of the frequency of disinfectant use with asthma control as measured by the Asthma Control Test (ACT). To date, over 1000 individuals have responded. Of those, 92% are based in the US, 80% are female, about 21% indicated minority race/ethnicity, and 625 agreed to be contacted for follow-up research. Of those willing to be contacted about, 40% had ACT≤19. About 95% of respondents reported increased hand washing, 88% increased use of alcohol-based hand sanitizer since the

[figure not shown]
[figure not shown]

Figure 2. Household use of Disinfectants ≥5 Times/Week prior To and Since COVID-19

COVID-19 pandemic (Figure 2); about one-third noted increased smoking behaviors by household members. The percentage of participants reporting household use of disinfectant wipes, disinfectant sprays, and a bleach and water solution to disinfect objects ≥ 5 times per week more than doubled since COVID-19. We observed statistically significant associations of the increased frequency of household disinfectants use since COVID-19 with reduced asthma control (ACT score ≤ 19).

Chicago Asthma Consortium (CAC) was formed in 1996 by American College of Chest Physicians and Respiratory Health Association to coordinate the activities of the asthma community in Chicago. One priority of the CAC is the coordination of the Community Advisory Board (CAB), which was formed in 2014 with support from several grants. The CAB is comprised of community health workers, parents, patients, and pastors from the communities that have the highest asthma rates in Chicago. The research team met with the 5 members of CAC on Wednesday August 5, 2020. The study was briefly explained to CAC members and feedback was received related to all aspects of the proposed protocol including adding an instructional video, reducing the routine EMA notifications from 3 to 2X/day, the 14-day data collection length, and assuring a research team member was available for troubleshooting. Suggestions were incorporated into the study procedures. Once funded, we will meet with the CAC semi-annually for input and feedback on study protocols, measures, recruitment, and interpretation of findings.

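### Entry requires use of at least 5 per week and ACT of 19 or below, so Aim 3's baseline use contrast has no designed unexposed group and Aim 2a's person-level prevalence is nearly fixed

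*Combined protocol and SAP*

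**What the plan says.** The Sample section limits entry to respondents of the earlier online survey (GCAS) who "reported high use of disinfectant/cleaning products since COVID-19 (≥ 5 per week), and current ACT ≤ 19". It continues: "Fifty individuals meeting these criteria will be randomly selected and invited to participate in this study". Those interested go to a survey link to "confirm willingness to participate, verify eligibility, and provide current contact information". There is no low-use or well-controlled comparison group.

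Under Data Analysis, Aim 3 lists three exposure variables. The first is "Baseline self-reported use and frequency of disinfectant/cleaner use", together with baseline PM2.5 exposures. The second and third are monitor readings: weekly counts of VOC and PM2.5 exceedances, and average levels per time window. The outcomes are any asthma symptoms, inhaler use and FEV1% predicted around each prompt. Aim 2a states: "We will determine the prevalence of disinfectant/cleaner use and frequency", with frequency defined as the percentage of EMA prompts at which use is reported.

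The EMA survey items include a Yes/No question, at two random prompts per day, on disinfectant or cleaner use over the preceding two hours. Aim 3 does not list it as an exposure. The Data Analysis section does not mention the entry restriction.

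**The concern.** The variable used to select participants reappears as an exposure. If everyone enrolled is a frequent user, baseline use is Yes for all and there is nobody to compare them with. Frequency can vary only from 5 per week upward. Entry is also restricted on ACT, which (Baseline Measures) covers symptoms and rescue medication and so overlaps two of Aim 3's three outcomes.

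This matters because the first exposure is the only self-reported disinfectant exposure that Aim 3 lists, and Aim 3 promises associations for self-reported as well as objective measures. The Preliminary work section reports that more frequent use went with ACT of 19 or below. A sample selected on both variables is a poor place to test that association. The Specific Aims say that the findings feed a powered study, and the Summary says that they may affect recommendations on disinfectant use. A weak baseline coefficient or a prevalence near 100% therefore needs its condition stated.

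**Working it through.** The documents give no power, effect size or sample-size calculation, so there is no stated figure to reproduce. Values marked assumed are not in the documents.

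**1. Baseline use, Yes/No.** If the entry criterion still holds at baseline, 0 of 50 are unexposed and the coefficient does not exist. In the criterion, the word for current status attaches to ACT and not to use, so a few people may have stopped since the survey. With k non-users, the person-level difference detectable with 80% power (two-sided 5%, unadjusted, in SD units) is (1.960 + 0.842) × √(1/k + 1/(50 − k)).

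| Non-users k (assumed) | Detectable difference (SD) |
|---|---|
| 1 | 2.83 |
| 5 | 1.32 |
| 10 | 0.99 |
| 25 (balanced, for scale) | 0.79 |

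A handful of lapsed users does not rescue the contrast.

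**2. Baseline frequency.** I simulated trivariate normal data (4 million draws) for exposure X, an ACT-like measure of poor control A, and outcome Y. The true X–Y correlation was set at 0.30. The sample kept the top 30% or 50% on X (assumed; the share is not stated) and the worst 40% on A. The 40% comes from Preliminary work: "Of those willing to be contacted about, 40% had ACT≤19". Power uses Fisher's z: Φ(√47 × atanh r − 1.960) + Φ(−√47 × atanh r − 1.960). For r = 0.12 this is √47 × 0.1206 = 0.827, giving 0.129 + 0.003, or about 13%. For r = 0.30, unselected, it is 56%.

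| X–A corr. (assumed) | A–Y corr. (assumed) | Users kept | Slope (true 0.30) | Correlation | Power, n = 50 |
|---|---|---|---|---|---|
| 0.30 | 0.7 | top 30% | 0.18 | 0.12 | 13% |
| 0.30 | 0.7 | top 50% | 0.18 | 0.14 | 16% |
| 0.30 | 0.3 | top 30% | 0.26 | 0.15 | 18% |
| 0.30 | 0.3 | top 50% | 0.26 | 0.17 | 22% |
| 0.20 | 0.7 | top 30% | 0.22 | 0.14 | 17% |
| 0.20 | 0.7 | top 50% | 0.21 | 0.17 | 21% |
| 0.20 | 0.3 | top 30% | 0.27 | 0.15 | 18% |
| 0.20 | 0.3 | top 50% | 0.27 | 0.18 | 23% |

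Selecting on X alone leaves the slope at about 0.30 and lowers the correlation to 0.16–0.19, which is a loss of precision and not a bias. Adding selection on A also lowers the slope, to 0.18–0.27.

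**3. Aim 2a.** There are 14 × 2 = 28 random prompts, each looking back 2 hours in a 16-hour day (6 a.m. to 10 p.m.). Assume f uses per week at independent random times and every prompt answered. Then P(Yes at a prompt) = p = 1 − (1 − 2/16)^(f/7), and P(any Yes) = 1 − (1 − p)^28.

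| Uses per week (assumed) | Prompts positive | P(any Yes in 28) |
|---|---|---|
| 5 | 9% | 93% |
| 7 | 12.5% | 98% |
| 14 | 23% | 99.9% |
| 21 | 33% | about 100% |

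Person-level prevalence is 93% or more for anyone at or above the entry level. The percentage of prompts still varies more than threefold.

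**4. Within-person information already collected.** The same rates imply 28 × 0.091 = 2.5 to 28 × 0.330 = 9.2 positive prompts per person. Each person therefore supplies both exposed and unexposed prompts, and selection on average use does not remove that contrast.

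**The case against.** The restriction is deliberate and disclosed: the Innovation section names adults with sub-optimal control as the target group. Aim 3 is worded as exploration, no power is claimed anywhere, and even an unselected sample of 50 has only 56% power in the illustration. Two of the three exposures come from the monitor, and window averages already vary within person. All of this stands. It lowers the severity, but it does not make a contrast without unexposed people estimable.

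A reader might infer more than the documents support:

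- *That selection determines the whole first exposure.* It does not. Frequency can vary above 5 per week, and the baseline PM2.5 exposures in the same item are not selected on.
- *That baseline frequency is constant because the form reuses a top category of at least 5 per week.* The form is not shown, so this cannot be asserted.
- *That the sample is cut on the outcome.* ACT is not an Aim 3 outcome. It overlaps symptoms and inhaler use, but none of its described content is lung function. Cutting on the outcome itself would take 0.30 to 0.11–0.13 with 12–14% power, which is slightly worse than the plan warrants.
- *That everything in Aim 2a is an entry condition.* Only person-level any-use is nearly fixed.
- *That the authors will report a null as no association, or apply the prevalence to all adults with asthma.* No text says so. The risk is an unlabelled result, not a stated intention.

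**Conclusion.** The point holds in a limited form. The baseline use/non-use contrast is essentially not estimable, and this follows directly from setting eligibility beside Aim 3. The near-fixed person-level prevalence in Aim 2a follows from the same criterion, with its size (93% or more) resting on the assumed prompt model.

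The between-person association for baseline frequency is range-restricted and probably attenuated. A true correlation of 0.30 becomes about 0.12–0.18, with roughly 13–23% power at n = 50. Those figures rest on normality, the assumed share of high users, the assumed correlations, and one summary value per person in place of the planned multilevel models. They show scale and do not predict the result. Because Aim 3 is exploratory, this should be fixed before analysis but does not undermine the study.

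**What to change.** - **Aim 3:** drop the baseline use/non-use contrast. Add EMA-reported use over the preceding 2 hours, from the random prompts, as a level-1 disinfectant exposure. Enter each prompt's value minus the person's mean, with the person's mean as a separate level-2 term, so that within- and between-person effects are not mixed. The level-2 term is subject to the same selection and should carry the same caution.
- **Baseline frequency:** it may stay as a continuous secondary exposure, labelled range-restricted, with a statement that a null is not evidence of no association. Removing it altogether would be a matter of preference.
- **Full range of use:** take any such between-person estimate from GCAS. Its contactable group alone shows the wider spread in control: "625 agreed to be contacted for follow-up research", of whom 625 × 0.40 = 250 had ACT of 19 or below, leaving about 375 above it if all gave an ACT. That estimate would concern ACT, not the EMA or spirometry outcomes.
- **Aim 2a:** report prevalence and frequency as applying to adults selected for at least 5 uses per week and ACT of 19 or below.

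**Cost:** wording in the analysis plan and one weak between-person contrast lost, with no new data collection. The main limit is coverage: two random prompts with a 2-hour look-back cover at most 4 of 16 hours per day, so use outside those windows is missed.
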